3. STUDY OBJECTIVES, ENDPOINTS, AND ESTIMANDS

3.1. Primary and Secondary Study Objectives and Endpoints

The primary and secondary study objectives and endpoints are:

Objectives	Endpoints
The primary objective is to evaluate the efficacy of TV-44749 in adult patients with schizophrenia.	
The primary efficacy endpoint is as follows:
 
 • The change from baseline to week 8 in the Positive and Negative Syndrome Scale (PANSS) total score.
A key secondary objective is to further evaluate the efficacy of TV-44749 based on additional parameters in adult patients with schizophrenia.	
The key secondary efficacy endpoints are as follows:
 
 • Change in Clinical Global Impression-Severity (CGI-S) scale score from baseline to week 8 • Change in Personal and Social Performance Scale (PSP) score from baseline to week 8
A secondary objective is to evaluate the safety and tolerability of TV-44749 in adult patients with schizophrenia.	
The safety and tolerability endpoints will include, where appropriate, the following: adverse events (including serious adverse events, extrapyramidal symptoms, injection pain and other injection site reactions [local tolerability]), vital signs (blood pressure, pulse and orthostatic changes, and temperature), body weight, laboratory tests, electrocardiogram (ECG), concomitant medication use, time to all-cause discontinuation, all-cause discontinuation rates and discontinuation rates due to adverse events (tolerability), and the following rating scales:
 
 • Abnormal Involuntary Movement Scale (AIMS) • Simpson-Angus Scale • Barnes Akathisia Rating Scale • Columbia Suicide Severity Rating Scale (C-SSRS) • Calgary Depression Scale for Schizophrenia (CDSS)

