At visits 2 and 7, the PANSS, Columbia Suicide Severity Rating Scale (C-SSRS), CGI-S, and Clinical Global Impression-Improvement (CGI-I; visit 7 [week 4] only) scales should be completed prior to investigational medicinal product (IMP) administration; all other scales and questionnaires may be completed either prior to IMP administration or after. Any assessments performed after IMP administration must be completed on the day of IMP administration.

Prior to screening, patients can be either outpatients or inpatients. All patients will be hospitalized upon study entry (screening) and will remain hospitalized during the screening period and for the first 4 weeks after randomization (until the second IMP administration). After the second injection, patients may be discharged if all discharge criteria are met and if, in the opinion of the investigator, discharge is appropriate. During the hospitalization period (ie, before the patient is discharged), a short-term leave from the site may be allowed if requested by the patient. Patient's eligibility for such leave will be determined by the investigator clinical judgment, in accordance with the study conduct and with the patient's best interest. During the leave, the patient will be escorted by a caregiver or another individual per investigator approval. The patient will return to the site on the same calendar day. In exceptional cases, an overnight stay outside the site may be approved by the investigator. Upon return to the site, after any period of leave, the patient will undergo a urine drug screen, an abbreviated physical examination (including weight), and a concomitant medication and alcohol consumption/illicit drug use inquiry. The results of these assessments, along with the date and time of site leave and return, will be captured in a dedicated case report form (CRF).

The Readiness for Discharge Questionnaire (RDQ) will be used to assess a patient's readiness for discharge ([Potkin et al 2005](#)) and should be completed by a qualified health care professional (HCP) who has a thorough knowledge of the patient's clinical condition, and has been following them throughout the duration of the hospitalization. The RDQ consists of 6 items, as presented below.

Discharge Criteria (RDQ):

1. The patient is not actively suicidal or homicidal.
2. The patient has adequate control over aggression and impulsivity.

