
Procedures and assessments that need to be performed after randomization into Period 2 at visit 11 (week 8) are as follows:

- IMP administration
- Blood samples for plasma concentration of IMP at 2.5 to 3 hours postdose

Remaining procedures and assessments at visit 11 (week 8) may be performed either before or after randomization.

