- Abnormal Involuntary Movement Scale (AIMS)
- Barnes Akathisia Rating Scale (BARS)
- Simpson-Angus Scale (SAS)
- Columbia Suicide Severity Rating Scale (C-SSRS)
- Personal and Social Performance Scale (PSP)
- Schizophrenia Quality of Life Scale (SQLS)
- [REDACTED]
- Calgary Depression Scale for Schizophrenia (CDSS)
- [REDACTED]
- Adverse events inquiry (including serious adverse event reporting and injection site related events [including pain])
- Inquiry regarding alcohol consumption/illicit drug use
- Cigarette use assessment
- Site confinement (for patients who are not already hospitalized)
- Concomitant medication inquiry

2. Procedures During Double-blind Treatment Period (Acute Treatment Phase; Period 1)

All patients will be hospitalized upon study entry (screening) and will remain hospitalized during the screening period and for the first 4 weeks after randomization (until the second investigational medicinal product [IMP] administration). After the second injection, patients may be discharged if all discharge criteria are met and if, in the opinion of the investigator, discharge is appropriate. During the hospitalization period (ie, before the patient is discharged), a short-term leave from the site may be allowed if requested by the patient. Patient's eligibility for such leave will be determined by the investigator clinical judgment, in accordance with the study conduct and with the patient's best interest. During the leave, the patient will be escorted by a caregiver or another individual per investigator approval. The patient will return to the site on the same calendar day. In exceptional cases, an overnight stay outside the site may be approved by the investigator. Upon return to the site, after any period of leave, the patient will undergo a urine drug screen, an abbreviated physical examination (including weight), and a concomitant medication and alcohol consumption/illicit drug use inquiry. The results of these assessments, along with the date and time of site leave and return, will be captured in a dedicated case report form (CRF).

a. Procedures for Baseline/Visit 2 (Day 1, Week 0)

Patients who meet the inclusion and exclusion criteria at visit 1 will continue to visit 2, when baseline assessments will be conducted.

The following procedures and assessments will be performed at visit 2:

- Inclusion and exclusion criteria
- Clinical laboratory tests (serum chemistry, hematology, and urinalysis)
- Randomization
- Urine drug screen

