Randomized patients should have a PANSS total score between 80 and 120, inclusive, at baseline (prior to randomization) with a score ≥ 4 on at least 2 of the following 4 items of the PANSS positive subscale: hallucinatory behavior, delusions, conceptual disorganization, or suspiciousness/persecution.

Patients demonstrating a reduction in the total PANSS score of $\geq 20\%$ between screening and the baseline (randomization) visit will not be eligible for randomization into the study.

Randomized patients will be treated with sc injections of TV-44749 (low [318 mg q1m], medium [425 mg q1m], or high dose [531 mg q1m]) or placebo at visit 2 (week 0) and visit 7 (week 4).

At visits 2 and 7, the PANSS, Columbia Suicide Severity Rating Scale (C-SSRS), CGI-S, and Clinical Global Impression-Improvement (CGI-I; visit 7 [week 4] only) scales should be completed prior to investigational medicinal product (IMP) administration; all other scales and questionnaires may be completed either prior to IMP administration or after. Any assessments performed after IMP administration must be completed on the day of IMP administration.

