The PANSS, C-SSRS, CGI-S, and CGI-I scales should be completed prior to IMP administration; all other scales and questionnaires may be completed either prior to IMP administration or after (except for visit 11 [week 8], where all assessments must be completed prior to IMP administration). Any assessments performed after IMP administration must be completed on the day of IMP administration.

For the entire duration of Period 2 (including any phone visits), a window of ± 3 days will be allowed around the scheduled visit dates for dosing visits; for any patients who are inpatients at the beginning of Period 2, every effort will be made to maintain the assessments on the scheduled dates during the inpatient period. Visit dates should be calculated from the date of previous IMP administration. In exceptional cases, per the discretion of the investigator and with permission from the MM or sponsor, dosing visits may take place up to 5 days before the scheduled visit date (and recorded accordingly).

Patients entering Period 2 will be treated for up to 48 weeks. An end-of-treatment (EOT) visit will be completed 4 weeks after the patient's last injection. The time window for the EOT visit is ± 1 week.

Dose Adjustment:

During Period 2, the investigator may perform dose adjustments of TV-44749 (to one of the doses offered in the protocol) from visit 12 (week 12) and onward, based on clinical judgment. Dose adjustment will be documented in the CRF.

Detailed procedures regarding dose adjustments will be provided in the pharmacy manual and in any other study plans as applicable.

Procedures for Potential Post-injection Delirium/Sedation Syndrome (PDSS)

[REDACTED]

Early Termination and Follow-up Period

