4.2. Specification of Baseline Values

For Period 1, the baseline value for a patient is the last observed data that was collected for this patient prior to the first IMP dose administration, unless otherwise noted.

For Period 2, the baseline value for a patient is the last observed data that was collected for a patient prior to the third IMP administration (i.e., first administration in period 2, at visit 11, week 8), unless otherwise specified (see procedures and assessments which may be performed after the re-randomization to Period 2 at visit 11 in Section 6.9.1 in the study protocol).

For the integrated periods to be presented in the CSR and during the IDMC closed (in an unblinded manner) and open (in a blinded manner) sessions, the baseline values of patients initially randomized in Period 1 to TV-44749 groups will be defined as the last observed data that was collected prior to the first TV-44749 dose administration. For patients that were assigned to placebo group in Period 1, the baseline value is the baseline value for Period 2 (see above paragraph).

It should be noted that the baseline values of placebo patients will differ between tables presented in the integrated periods summaries and those presented in Period 1 summaries.

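### At visit 2 PSP and five other scales may be rated after the first injection, but the SAP baseline rule then discards that rating and falls back to screening

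*Protocol*

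**What the plan says.** **Order at visit 2.** Protocol 4.1 (Period 1) and Table 1 footnote aa name the scales that must precede the injection: PANSS, C-SSRS and CGI-S, with CGI-I added at visit 7. For the rest, "all other scales and questionnaires may be completed either prior to IMP administration or after". The only limit is "Any assessments performed after IMP administration must be completed on the day of IMP administration". SAP 2.1 carries the same rule: the named scales are to be "completed prior to investigational medicinal product (IMP) administration; all other scales and questionnaires may be completed either prior to IMP administration or after".

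**Baseline.** SAP 4.2 gives the Period 1 rule as follows: "the baseline value for a patient is the last observed data that was collected for this patient prior to the first IMP dose administration", with a general proviso for exceptions noted elsewhere. The visible PSP sections (SAP 6.3.2 and 6.3.8) note none.

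**Status of PSP.** Protocol 3.1 lists "Change in Personal and Social Performance Scale (PSP) score from baseline to week 8" as a key secondary endpoint. Table 1 schedules PSP at screening, visit 2, visit 7 and visit 11. SQLS, CDSS, AIMS, BARS and SAS are also scheduled at both screening and visit 2.

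**Precedence.** Protocol section 10 and the SAP introduction both say that the SAP prevails where the two differ.

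**Visit 11.** Protocol 6.9.1 lists PSP, CDSS, AIMS, BARS and SAS, but not SQLS, among the items due before Period 2 randomization, and adds "Remaining procedures and assessments at visit 11 (week 8) may be performed either before or after randomization". SAP 2.1 describes visit 11 as the visit "where all assessments must be completed prior to IMP administration".

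**The concern.** The plan permits a visit 2 rating that its own baseline rule then rejects. For PSP the rejected value is the baseline of a key secondary endpoint: it enters the change score, and SAP 6.3.8 names it as a model covariate. Whether a patient's baseline is the Day 1 or the screening value would depend on the order in which a site happened to work that day.

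It looks like an oversight. At visit 11 the protocol places PSP before re-randomization, and dosing follows randomization, so the order is fixed at the endpoint but not at baseline. SAP 4.2 points to Protocol 6.9.1 for visit 11 items that may follow re-randomization, but has no parallel note for visit 2.

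At stake is a clean, uniform baseline for PSP, and for the five other scales, with some precision in the PSP comparison. PANSS and CGI-S are not affected, because they must precede the dose.

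**Working it through.** The plan gives no figure for this point, and the sample-size inputs are redacted. The check is mainly a reading of the rules, followed by an illustrative calculation.

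**Step 1. Follow two patients through the rules.**

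| | PSP rated before the injection on Day 1 | PSP rated after the injection on Day 1 |
|---|---|---|
| Allowed by Protocol 4.1, footnote aa, SAP 2.1? | Yes | Yes |
| Day 1 value eligible under SAP 4.2? | Yes | No |
| Last eligible value | Day 1 | Screening |
| Age of baseline at first dose | 0 days | Up to 8 days; up to 10 if screening is extended |

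**Step 2. Ask what state the screening value represents.** Protocol 4.1 says that the taper of prior oral antipsychotics should finish before randomization, but does not place the screening PSP before or after it. Patients without olanzapine in the past year take two oral doses during screening, and only PANSS and CGI-S must precede those doses. The screening PSP therefore has no fixed position relative to either event.

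**Step 3. Size of the precision loss, under assumptions.** The documents give neither the affected share nor the correlations. Assume:
- correlation of baseline with week 8 PSP: 0.5 for a Day 1 baseline, 0.4 for a screening baseline;
- share *p* of patients with a post-dose visit 2 rating: 10%, 30% or 50%.

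After adjustment for a baseline with correlation *r*, the residual variance is proportional to 1 − *r*²:
- Day 1: 1 − 0.25 = 0.75
- Screening: 1 − 0.16 = 0.84

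With a mixture, the variance is (1 − *p*) × 0.75 + *p* × 0.84, and the standard-error ratio is the square root of that over 0.75:
- *p* = 10%: 0.675 + 0.084 = 0.759; √(0.759/0.75) = 1.006
- *p* = 30%: 0.525 + 0.252 = 0.777; √(0.777/0.75) = 1.018
- *p* = 50%: 0.375 + 0.420 = 0.795; √(0.795/0.75) = 1.030

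The model has one baseline slope for everyone. If both baselines have the same mean and variance, the variance becomes 1 − (0.5 − 0.1*p*)². At *p* = 10% this is 1 − 0.49² = 0.7599, ratio 1.007; at *p* = 50% it is 1 − 0.45² = 0.7975, ratio 1.031. The conclusion does not change.

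**Step 4. Check whether the rule differs by arm.** It does not. The timing permission is identical in all four arms, Period 1 raters are blinded, and under SAP 4.2 every baseline, whether Day 1 or screening, precedes the first dose.

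**The case against.** The strongest reply is that SAP 4.2 already resolves the matter: baseline is the last pre-dose value, a screening PSP exists, and the SAP prevails. The fallback is then defined, the same in all arms, and costs at most a few percent of standard error on assumed inputs. The affected share could be near zero. Most of this stands. It limits the harm but does not remove the conflict, since the SAP itself both allows the late rating and excludes it.

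Four stronger readings are tempting and are not supported:

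- **An on-drug baseline in the active arms.** A reader might infer that post-injection PSP, AIMS, BARS or SAS values become baseline. Under SAP 4.2 they do not. That would need selection by visit label or by date alone, which departs from the SAP. The SAP does leave room for the slip: section 4.4 defines Day 1 by the dosing date and gives no time-of-day rule, and Protocol Appendix B treats visit 2 as the baseline visit.
- **Bias in the PSP comparison.** Within-arm change for affected patients would absorb any movement between screening and Day 1, but the tested quantity is the difference from placebo, and nothing makes the fallback differ by arm.
- **A screening PSP taken before the taper and before oral olanzapine.** No passage says so.
- **Week 8 SQLS rated after the third injection, the first active dose for placebo patients.** Section 6.9.1 speaks of before or after randomization, not injection. Protocol 6.9 and SAP 2.2 put Period 2 assignment after all visit 11 scales, and Table 1 footnote cc and SAP 2.1 put all assessments before dosing. What remains is a wording mismatch.

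It is also fair to object that reordering visit 2 comes late. The protocol amendment reports 675 patients randomized by 29 January 2024 against about 640 planned, and SAP 6.1 says that the later active-only enrolment was not exercised.

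**Conclusion.** The conflict is real and can be read directly from the text. For any patient whose PSP, SQLS, CDSS, AIMS, BARS or SAS was rated after the first injection, the Day 1 value is lost as baseline and a screening value up to 8 to 10 days old takes its place.

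For PSP the result is a mixed baseline and a small loss of precision, about 0.6% to 3% in the standard error across the range shown. That range rests entirely on the assumed share and correlations; the true share depends on site practice. The point is worth correcting because a key secondary baseline should not turn on site habit, but it does not threaten the validity of the PSP treatment comparison.

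**What to change.** 1. **Patients not yet dosed, if any.** In Protocol 4.1, Table 1 footnote aa and SAP 2.1, require PSP, SQLS, CDSS, AIMS, BARS and SAS at visit 2 before IMP administration, as for PANSS and CGI-S.
2. **Patients already dosed.** In the SAP, compare the eCOA time stamp with the injection time, flag visit 2 values rated post-dose, and state that section 4.2 governs them. Report the number flagged by arm. Protocol Appendix M lists all six scales as eCOA. That both times were recorded is an assumption, though the timed post-injection pain and blood-sample assessments need an injection time.
3. **One PSP sensitivity analysis that keeps all randomized patients**, for example with the same-day visit 2 value as baseline for flagged patients. Dropping them would depart from the all-randomized analysis set.
4. **Visit 11.** Align the 6.9.1 wording on SQLS with SAP 2.1 and Table 1 footnote cc, so that all assessments precede IMP.

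The cost is one extra table and a few lines of text, with no new assessments. SAP 2.6.2 allows amendments approved before the first database lock, so items 2 and 3 fit that route. Since enrolment appears complete, they carry most of the remaining value.

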4.2. Planned Number of Patients and Countries

Approximately █ patients will be screened to achieve approximately 640 randomized patients. Following the primary efficacy estimand, all randomized patients will be evaluable for efficacy analysis in this study. Details on definition of evaluable patients and sample size are given in Section 10.

The study is planned to be conducted in the US, Bulgaria, █, Romania, █, Turkey, and possibly other countries, in approximately 100 investigational centers. The study is expected to start in Q4 2022 and last until approximately Q2 2025.

4.3. Justification for Study Design and Selection of Population

Schizophrenia is a lifelong illness with evolving symptoms that can fluctuate in severity over time. A major goal in designing treatments for schizophrenia is to effectively stabilize symptoms, keep them stable over the long term, and maintain an acceptable safety profile. The

present study is designed to assess the ability of TV-44749 to stabilize symptoms in a patient population with unstable symptomatology experiencing an acute exacerbation of schizophrenia. The study will evaluate the efficacy of TV-44749 on psychiatric symptoms, relative to placebo. It will also assess the safety and tolerability of TV-44749 in patients with schizophrenia over a treatment period of 56 weeks.

Refer to Section 6.3 for the justification of the IMP dose and the use of placebo IMP and to Section 3.1.1 for the justification of the primary endpoint.

4.3.1. Study Duration

Registration trials for drugs indicated for schizophrenia, in patients experiencing an acute symptom exacerbation, are typically randomized, double-blind, placebo-controlled studies, 6 to 8 weeks in duration. This is because thus far, for second-generation antipsychotics, a reasonable stability of effect is often observed (as well as some effect on negative symptoms) only after 6 weeks of treatment ([Gopalakrishnan et al 2021](#)).

In case of LAIs, the selection of the timing for the primary endpoint should take into consideration the dosing interval of the LAI under investigation as well as the anticipated onset of therapeutic effect. For instance, the confirmatory efficacy trial for the recently approved LAI risperidone product PERSERIS® (Indivior Inc.) used mean change from baseline to week 8 in the PANSS total score as the primary efficacy endpoint, aligned with the q1m administration regimen of the investigational product ([Nasser et al 2016](#)).

Similarly, as TV-44749 is an LAI intended for q1m administration, this study is designed as a randomized, double-blind, placebo-controlled study in patients with acute exacerbation of schizophrenia, comparing 3 dose strengths of TV-44749 q1m with placebo q1m with a primary endpoint of change from baseline to week 8 in the PANSS total score, with a long-term safety period.

Shorter study duration (eg, 4 weeks) could also be considered, especially given the fact that TV-44749 has a similar profile to existing antipsychotic drugs. However, this carries the risk of negative results if maximal therapeutic effect is not obtained at 4 weeks, and the shorter duration is disadvantageous in terms of the ability to demonstrate stability of effect.

4.3.2. Patient Selection

This study will enroll patients diagnosed with schizophrenia according to the criteria of Diagnostic and Statistical Manual of Mental Disorders, 5th Edition (DSM-5). The diagnosis will be confirmed using a structured assessment tool (Structured Clinical Interview for DSM-5, Clinical Trials Version [SCID-5-CT]).

The acute status will be confirmed by the total PANSS score between 80 and 120, inclusive, at screening and baseline (prior to randomization), with a score ≥ 4 on at least 2 of the following 4 items of the PANSS positive subscale: hallucinatory behavior, delusions, conceptual disorganization, or suspiciousness/persecution, and a CGI-S score of ≥ 4 (moderately ill) at screening and baseline (prior to randomization).

Further descriptive parameters, demographic characteristics, and a detailed disease history, such as age, sex, ethnicity, age at onset of illness, duration of current episode, baseline psychopathology, comorbid conditions, substance abuse, etc will be documented.

Exclusion of patient groups that may introduce confounding factors (eg, comorbidities or concomitant medication as detailed in study exclusion criteria) will maximize external validity and broad applicability to the intended patient population without unduly compromising internal validity.

